Application of RECELL to Promote Healing Following CO2 Laser
Treatment in Cosmetic Facelift Patients

IRB00085278

NCT05386368

IRB Approval Date: 05/04/2023

Study Title: Application of RECELL to Promote Healing Following CO2 Laser Treatment in Cosmetic Facelift Patients

Principal Investigator: [name], PhD

Co-investigator(s): [name], PhD, [name], [name], [name], [name], BA, [name], [name], BS

Sponsor or funding source: Department of Plastic and Reconstructive Surgery, RECELL product provided by Avita Medical

Background, Rationale and Context

The RECELL system is a regenerative epidermal harvesting device that is currently FDA approved for use in treatment of partial thickness burns in adults. The system works by enzymatically processing a small sample of the patient's skin to create a regenerative epidermal suspension (RES) graft that can be sprayed onto a burn wound. Contained within the RES is a mix of keratinocytes, fibroblasts, and melanocytes.^{1,2} The advantage of using the RECELL system over traditional skin grafting techniques is that, when enzymatically processed, donor tissue can be applied to re-epithelialize a significantly larger area than traditional skin grafting techniques. RES usually allows an 80:1 donor site to graft site expansion ratio.^{3,4}

While RES has been most extensively used in burn treatment, it has also been used with success following CO2 laser resurfacing for the treatment of vitiligo and for enhanced healing following microdermabrasion.^{5,6} A decade of precedent exists for treating patients with vitiligo through a combination of CO2 laser and regenerative epidermal suspension grafting with the goal of improved skin pigment after re-epithelialization.⁷ A 2019 study assessed the healing time with and without RECELL application in 78 patients undergoing microdermabrasion for acne scar treatment. They study found a statistically significant decrease in healing time between the two groups, with the RECELL group (n = 48) healing in an average of 5.27 days and the group with microdermabrasion alone (n= 30) healing in an average of 12.3 days; healing time was defined as total epithelialization duration.⁸

With the safety and efficacy of RES demonstrated in multiple clinical contexts, our study aims to ascertain if RES can be used for cosmetic purposes to enhance healing following CO2 partial field ablation. CO2 laser resurfacing is often used as an adjunct treatment during facelift procedures to address signs of aging in the periorbital and perioral areas. The laser treatment works by a superficial layer of the skin, requiring complete reepithelialization of laser treated areas. This process results in significant post-operative erythema, pain, and downtime for the patient. During the facelift procedure, excess skin is removed and discarded. In our proposed study, this excess skin would be repurposed via processing with the RECELL system to be used as a regenerative epidermal suspension graft on CO2 laser treated areas. The excess skin removed on a facelift is a greater surface area than the required 2 x 3 skin graft that is required for the common 80:1 expansion used in burn surgery. Therefore, we should have significant amounts of excess skin that could be repurposed as a split thickness skin graft that can be used for the recell. There will not be any additional skin removed further than what is required for the

facelift. We will use an 0.008 inch Weck blade to repurpose the excess skin into a split thickness skin graft need for the recell.

Device Output Characterization

We do not have any plans for this.

Objectives

The primary objective and study endpoint will be safety. The number of skin reactions will be evaluated to measure the primary endpoint over the treated area vs placebo control.

Methods and Measures

Design

Randomized, Double Blind, Placebo Controlled

Setting

Atrium Health Wake Forest Baptist Department of Plastic and Reconstructive Surgery

Subjects selection criteria

- **Inclusion Criteria**

- Adults 22 years or older

- Patients undergoing facelift with perioral CO2 laser treatment

- Skin that is Fitzpatrick Score 1 or 2

- Subjects who are in general good health

- Subjects who fully understand the research nature of this study and sign the informed consent

- **Exclusion Criteria**

- Prior perioral CO2 laser resurfacing

- Allergy to components of preparation system

- Subjects who have cosmetic or surgical treatment in perioral area within 3 months before the study (including laser, chemical peels, fillers, botulinum toxin).

- Subjects with existing open wounds on the face

- Subjects with active cutaneous infection, acne, dermatitis or any active dermal disease on the face

- Subject with signs of hypersensitivity or inflammation on the face

- Subjects with known hypersensitivity to trypsin or compound sodium lactate solution (Hartmann's Solution)

- Subjects with known hypersensitivity to anesthetics, adrenaline/epinephrine, povidone-iodine, or chlorhexidine solutions.

- Subjects with any disease/condition that may affect wound healing such as diabetes or obesity

- Subjects with any bleeding disorder

Subjects with any existing malignancy
Subjects who are pregnant, breastfeeding, or whose urinary pregnancy test is positive before participation in the study
Subjects with any disease/condition deemed unsuitable for facelift surgery or RECELL treatment by the treating physician

- **Sample Size**
10 patients

Interventions and Interactions

The perioral area of the face will be treated with CO2 laser. Laser setting will be determined by the treating surgeon for each individual patient. The laser is a Lumenis Ultrapulse/Surgitouch CO2 laser, 510(k) Number K030147. A laser (light amplification by stimulated emission of radiation) based device having coherence, collimated and typically monochromatic radiation. Typically indicated to cut, destroy, remove or coagulate tissue, generally soft tissue, for general surgical purpose in medical specialties of general and plastic surgery, dermatology/aesthetic, podiatry, otolaryngology (ent), gynecology, neurosurgery, orthopedics (soft tissue), dental and oral surgery, and dentistry. The classification regulation 21 cfr 878.4810 describes a device that is carbon dioxide or argon laser intended to cut, destroy, remove or coagulate tissue by the light. This laser is typically used in our practice for skin resurfacing to reduce the signs of aging, improve skin texture, laxity and tone, and reduce scars and stretch marks. Typical settings to be used for severe facial photoaging with Total FX is: Active FX, Energy (mj) 100-125, Scan Size 6-7 mm, Density 2-3, Hertz 100-200, Repeat Delay 0.3-1.5 seconds, number of passes 2. Deep FX, Energy (mj) 12.5-22.5, Scan Size 10 mm, Density 5-20%, Hertz 300-600, Repeat Delay 0.3-1.5 seconds, Number of Pulses 1-2, number of passes 1-2. The patient would be randomized and blinded to either left perioral or right perioral RECELL application. The surgeon would also be blinded to which side received RECELL treatment or Placebo (saline spray). Randomization would occur before study initiation with subjects assigned either left perioral or right perioral RECELL treatment based on their subject enrollment number. The study team member who prepares and blinds the RECELL will create the list of subject ID numbers with subject ID number randomly assigned to either left perioral or right perioral treatment group. This will be completed prior to any patient enrollment in the study. This spreadsheet will be password protected and only accessible to study coordinators and the team member responsible for preparing RECELL.

RECELL® is a single-use, stand-alone, battery-operated, regenerative epidermal harvesting device containing enzymatic and delivery solutions, sterile surgical instruments, and actuators. The cell suspension contains a mixed population of cells, including keratinocytes, fibroblasts, and melanocytes, obtained from the disaggregation of the skin sample. The Enzyme used to process the cells is a biological agent and as such may have slight variations in color and texture. The enzyme is derived from animal tissue and has undergone filtration and terminal sterilization by gamma irradiation.

Intraoperatively, RECELL and Placebo will be provided to surgeons and assistants in opaque application devices prepared by a trained, designated study team member.

Both the treatment and placebo sides, will be dressed with a standard regenerative epidermal suspension post treatment dressing (Telfa Clear and Xeroform). Xeroform will be removed on postoperative day 1. Telfa clear will be removed on postoperative day 7. Patients will return to clinic for follow up at the following interval:

- Post Operation Day 1
- Post Operation Day 7
- Post Operation Day 14
- 1-month Post Operation
- 2-months Post Operation
- 3-months Post Operation

There is always a chance the patient may need to be withdrawn from the study. The main consideration for stopping is the dressings, as the Recell will already be sprayed. If the patient cannot tolerate the dressings, we will stop and remove them from the study. Otherwise, we will deal with complications similar to how we would deal with other laser reactions- local wound care, anti-virals, etc.

Any signs of anaphylactic events will lead to the study stopped immediately and unbinding. We will immediately wash the cell suspension off of the face with 3 liters of normal saline (NS) while treating the anaphylaxis per institutional protocol (including submuscular epinephrine).

Any high incidence of serious adverse events (any serious adverse event, including severe infection requiring return to the operating room) will warrant early unbinding and assessment of safety immediately.

Subjects will be able to withdraw from the study for any reason and at any time. We can remove the cell suspension with removal of dressings and 3 liters of NS wash.

Outcome Measure(s)

Preoperatively patient baselines will be established with standardized studio photographs, and photos using the Quantificare LifeViz® Camera, as well as in person evaluation.

Intraoperatively, the patient will be photographed in CO2 treated areas with the Quantificare LifeViz® Camera and standardized photography. This camera measures lines, closing surfaces, volume, depth, and perimeter of the skin surface for microstructure analysis. We will analyze this data to track progress throughout the study.

Postoperatively, patients will be evaluated at each visit via in person evaluation by the surgeon, as well as using standardized photography, Quantificare LifeViz® Camera photos, administration of applicable FACE-Q scales (patient completed survey), and pain score (standard 1-10 pain scale). Please find FACE-Q scales in Appendices B-H.

Please find study calendar in Appendix A.

Analytical Plan

Results will be analyzed initially using descriptive statistics. Comparison between groups will be done using Fisher's exact tests for proportions, and t-tests or ANOVA procedures for continuous variables. Regression analysis will be performed to identify independent outcome predictors. Other inferential statistical analysis will be conducted as appropriate.

Human Subjects Protection

Collection of patient-identifying information will be limited to what is necessary to conduct analysis that is accurately linked to a given subject. Other than the master 'linkage' file, patient names, and medical record numbers will be removed and subjects will be associated with an abstracted unique Study ID. DOB will only be collected in order to dynamically calculate age at operative and follow up time points. Data will be stored electronically on the Wake Forest School of Medicine's secure REDCap server, a HIPAA-compliant web platform. Information for each subject will be entered directly from EPIC to the secure REDCap database, so data will not be stored on portable storage devices (including USB drives). In addition to study informed consent, photography consent will be obtained.

Subject Recruitment Methods

Patients who are scheduled to undergo elective facelift surgery with perioral CO2 laser resurfacing will be identified in the Plastic Surgery Clinics at both Janeway Tower and Vest Mill office locations. Any patient meeting inclusion criteria will be recruited during preoperative planning. Patients will have study information provided by a qualified study team member. There will be no compensation provided for this study, but the laser will be offered at no cost for participants.

Informed Consent

Informed consent will be obtained by approved study personnel after study purpose, duration, interventions, benefits and risks are thoroughly discussed with the subject. After the entire consent has been reviewed and all questions have been answered, potential subjects will be given the option to participate. A copy of the signed and dated consent form will be given to each enrolled subject and one placed on the chart. The original will be kept with research study records. In addition, a consent for photography and photograph use in research and publication will be obtained and placed in the chart prior to study participation. Please see a copy of Informed Consent in Appendix I.

Confidentiality and Privacy

Confidentiality will be protected by collecting only information needed to conduct outcomes research and related research to improve facelift and CO2 laser resurfacing outcomes. All database data will be entered into the Wake Forest School of Medicine's secure REDCap server. To help ensure subject privacy and confidentiality, a linkage file will be maintained containing each patient's medical record number and unique REDCap ID. Patient names will not be maintained in this file. The linkage file will be stored separately from the data available to researchers and will be kept secure, with access limited to designated study personnel. Data access will be limited to study staff. Data and records will be kept locked and secured, with any

computer data password protected. No reference to any individual participant will appear in reports, presentations, or publications that may arise from the study however patient photographs may appear in publications with patient consent.

Data and Safety Monitoring

The principal investigator will be responsible for the overall monitoring of the data and safety of study participants. The principal investigator will be assisted by other members of the study staff.

Additional safety assessment will include a full medical history and physical before proceeding with study activities.

Reporting of Unanticipated Problems, Adverse Events or Deviations

Adverse events would include the inability to tolerate dressings, deeper burns - including blistering burns or full-thickness burns - which would be managed with local wound care as we would manage any other burn in our burn center. We will record any viral outbreaks and any need for antivirals (such as HSV outbreaks from burn or recell). Given the fact that we are doing a controlled burn, the adverse outcome for "burns," will be blistering burn, signifying a deeper than expected burn from the laser.

We will assess for adverse events at each follow-up visit. Follow-up visits will include photography and assessment for adverse events.

Any unanticipated problems, serious and unexpected adverse events, deviations or protocol changes will be promptly reported by the principal investigator or designated member of the research team to the IRB and sponsor or appropriate government agency if appropriate.

We will report all adverse events to the FDA as described in 21 CFR 312.32.

Risk Analysis

Given that Recell is a product that speeds up wound healing, we do not anticipate that it will lengthen the wound healing course for the laser.

References

1. Hirobe T. Keratinocytes regulate the function of melanocytes. *Dermatologica Sin.* 2014;32(4):200-204. doi:10.1016/J.DSI.2014.05.002
5. Lommerts JE, Meesters AA, Komen L, et al. Autologous cell suspension grafting in

- segmental vitiligo and piebaldism: a randomized controlled trial comparing full surface and fractional CO2 laser recipient-site preparations. *Br J Dermatol.* 2017;177(5):1293-1298. doi:10.1111/bjd.15569

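### The opaque applicator stops masking once the fluid is on the skin, so the blind on the side-by-side skin-reaction count could break at application

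*Combined protocol and SAP*

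**What the plan says.** The Design section labels the trial "Randomized, Double Blind, Placebo Controlled". The Objectives section makes safety the primary endpoint: "The number of skin reactions will be evaluated to measure the primary endpoint over the treated area vs placebo control". It gives no scale or definition of a skin reaction and does not say who counts them.

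Interventions and Interactions sets out a split-face allocation ("The patient would be randomized and blinded to either left perioral or right perioral RECELL application") and states the intended masking of the operator: "The surgeon would also be blinded to which side received RECELL treatment or Placebo (saline spray". Later in the same section comes the means of concealment at application: "RECELL and Placebo will be provided to surgeons and assistants in opaque application devices prepared by a trained, designated study team member". The active product is described thus: "The cell suspension contains a mixed population of cells, including keratinocytes, fibroblasts, and melanocytes, obtained from the disaggregation of the skin sample". Both sides then receive the same dressing, and the allocation list is restricted to the coordinators and the person who prepares the product.

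Under Outcome Measure(s), "patients will be evaluated at each visit via in person evaluation by the surgeon", with standardized and LifeViz photographs also taken. No masked reading of the photographs is planned. The section on adverse-event reporting has events assessed at each follow-up visit, again without naming an assessor.

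**The concern.** Saying that the surgeon is blinded states an aim. The procedure has to deliver it, and an opaque device does so only until the fluid leaves it. From then until the dressings are on, a cell suspension lies on one side of the mouth and saline on the other, on one face and in one session. Those are good conditions for noticing even a small difference, and recognising one side reveals the other.

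At stake is the trial's only controlled safety comparison. With no definition of a skin reaction, what gets counted is partly a matter of judgement. An assessor who believes they know the RECELL side could, without intending to, record fewer or more reactions there. Under-recording on the active side would be the worse error in a safety study, because it would hide harm.

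**Working it through.** The point rests on the text and on no calculated figure. The sample size of 10 is given without a reaction rate, significance level or power, so there is no plan figure to reproduce.

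**Step 1: each masking measure against the interval from spraying to dressing**

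| Measure | What it protects | Hides the fluid on the skin? |
|---|---|---|
| Separate team member prepares both products | Knowledge from preparation | No |
| Opaque applicator | Fluid inside the device | No |
| Restricted allocation list | The assignment record | No |
| Same dressing on both sides | Appearance once dressed | Only after the spray has been seen |

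None covers that interval.

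**Step 2: are the people who may see the spray kept apart from the assessor?** The devices go to surgeons and assistants. The in-person assessor at each visit is the surgeon. Nothing assigns spraying to someone who does not assess, and nothing keeps the assessor from viewing the field.

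**Step 3: are the fluids said to match?** No. One is a suspension of mixed skin cells and the other is saline. The appearance of neither, once sprayed, is described.

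**Step 4: scale.** With 10 patients, one patient whose reaction is scored differently on one side changes that side's rate by 1/10 = 10 percentage points. This is true of any 10-patient comparison and does not estimate bias.

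**Step 5: an illustration on assumed inputs.** Suppose:
- a reaction is yes/no per side, with the same true probability p on both sides, independently;
- an unmasked assessor omits a share b of RECELL-side reactions;
- the 10 pairs are compared by an exact two-sided sign test at 0.05.

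The Analytical Plan names Fisher's exact test and no significance level, so the test and the level are my assumptions too.

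Five discordant pairs in one direction give 2 × 0.5^5 = 0.0625, and six give 2 × 0.5^6 = 0.031. At least six discordant pairs are therefore needed to reject.

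The probability of a reaction recorded on the placebo side only is p[1 − p(1 − b)]. On the RECELL side only it is p(1 − b)(1 − p). Summing the multinomial probabilities of all rejecting outcomes gives the false-positive rate. The expected spurious shortfall on the RECELL side is 10 × p × b.

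| p | Shortfall at b = 50% | False-positive rate, b = 0 | False-positive rate, b = 50% |
|---|---|---|---|
| 0.2 | 10 × 0.2 × 0.5 = 1.0 | 0.17% | 0.25% |
| 0.5 | 10 × 0.5 × 0.5 = 2.5 | 0.9% | 6.0% |
| 0.8 | 10 × 0.8 × 0.5 = 4.0 | 0.17% | 19.7% |

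Under these assumptions the count is biased at every reaction rate, while the test's error rate rises materially only when reactions are common.

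**The case against.** The strongest reply is that two links are missing from the text.

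First, a reader might infer that the surgeon who sprays is the person who scores the reactions. The documents do not say so. The devices go to surgeons and assistants, no one is named as applying them, and no assessor is tied to the primary count. This objection stands against the stronger reading. It does not remove the risk, because nothing separates the two roles and the surgeon is the only assessor named.

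Second, a reader might infer that the sprays look different, perhaps from the remark "may have slight variations in color and texture". That remark concerns the enzyme used in processing. It is not evidence about the final suspension or how it compares with saline. A visible difference is plausible from the composition but undocumented, so the surgeon could come to know the side; it cannot be said that the surgeon would. Seeing a difference would also have to reveal which spray was RECELL.

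It is fair to add that the identical dressings and restricted list are sound measures, and that several listed adverse events, such as blistering or full-thickness burns and viral outbreaks, are concrete enough to limit leniency. The photographs could allow a later check. But these measures do not hide the spray, the listed events are not stated to be the definition of a skin reaction, and no one is assigned to read the photographs masked.

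**Conclusion.** The concern holds in conditional form. If the sprays differ visibly and the evaluating surgeon sees them applied, the blind on the side-by-side skin-reaction count could break at time zero, and nothing in the protocol prevents it. Every one of the 10 patients would be exposed to that possibility.

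The documents do not support saying that the trial is unblinded, nor any estimate of the resulting bias. The false-positive rates above depend on assumed reaction rates, an assumed share of omitted reactions and a test the plan does not name. They show how such a bias could act and should not be read as a forecast. The change is worth making because the risk bears on the primary comparison and the remedy is small.

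**What to change.** In Interventions and Interactions and in Outcome Measure(s), state that:

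1. Whoever scores skin reactions is named by role and does not view the field from the start of spraying until both sides are covered. The protocol does not say whether the first dressing layer hides the fluid; if it does not, this period should run until the dressing is complete.
2. An assistant already present, who scores no outcome, sprays both sides and places the first dressing layer.
3. Any intraoperative photographs the assessor will see are taken after the laser and before spraying. The protocol does not at present give their timing relative to the spray.

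The cost is about a paragraph of text. The downside is that the evaluating surgeon does not apply the spray personally and steps back briefly. The protocol already provides for assistants, but the site should confirm that one can take this step.

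If that is not workable, similar protection would come from having reactions scored by an assessor absent from the application, or from coded copies of the postoperative photographs already planned, read by someone masked to side.

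### Patients who cannot tolerate the dressings are removed from the study after RECELL has been sprayed and, read naturally, would miss the later safety visits of a trial whose primary endpoint is safety

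*Combined protocol and SAP*

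**What the plan says.** All references are to the combined protocol and SAP.

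- **Removal rule (Interventions and Interactions).** "If the patient cannot tolerate the dressings, we will stop and remove them from the study". The preceding sentence explains the focus on dressings: "The main consideration for stopping is the dressings, as the Recell will already be sprayed". The patients concerned have therefore already been exposed.
- **Timing (same section).** Xeroform comes off on day 1, and "Telfa clear will be removed on postoperative day 7". There are six postoperative visits: days 1, 7 and 14, and months 1, 2 and 3.
- **Other exits (same section).** Dressing intolerance is not the only stop: "Any signs of anaphylactic events will lead to the study stopped immediately and unbinding". Patients may also withdraw at any time, and for voluntary withdrawal the text says "We can remove the cell suspension with removal of dressings and 3 liters of NS wash".
- **Endpoint (Objectives).** Safety is primary: "The number of skin reactions will be evaluated to measure the primary endpoint over the treated area vs placebo control". No time window is attached to this count.
- **Adverse events (Reporting of Unanticipated Problems, Adverse Events or Deviations).** "Adverse events would include the inability to tolerate dressings", and "We will assess for adverse events at each follow-up visit".
- **Analysis (Analytical Plan).** No analysis set is defined, and nothing is said about patients who leave early.

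The available text does not provide for study visits after removal. The study calendar (Appendix A) and consent form (Appendix I) are listed, but their content is not in that text.

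**The concern.** The rule ties two separate decisions together: stopping the dressings and leaving the study. The first concerns care. The second decides whether an exposed patient is still observed for the primary endpoint. If removal ends study visits, as the wording suggests, then reactions first appearing after removal are looked for in fewer than the 10 patients treated, and what sends a patient out is itself a listed adverse event.

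Each patient serves as their own control, with one perioral side receiving RECELL and the other saline. A removal therefore takes away both sides of one comparison. In a study of 10, each patient is a tenth of the safety evidence, and visits not made cannot be recovered afterwards.

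**Working it through.** The plan gives no figure to reproduce here. The sample size of 10 has no derivation, and no intolerance rate, reaction rate or dropout allowance is stated.

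**Inputs from the documents.** 10 patients (Sample Size); six postoperative visits, with Telfa Clear worn to day 7 (Interventions and Interactions).

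**Planned visits.** 10 × 6 = 60 patient-visits in all. Four visits fall after day 7, giving 10 × 4 = 40.

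**Visits lost per removal, if removal ends visits.** Intolerance can arise only while dressings are on, so removal would come by about day 7.

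| Time of removal | Visits lost | Share of 60, one removal | Share of 60, two at the same stage |
|---|---|---|---|
| At the day 7 visit | 4 | 4/60 = 6.7% | 8/60 = 13.3% |
| At or after the day 1 visit, before day 7 | 5 | 5/60 = 8.3% | 10/60 = 16.7% |
| Before the day 1 visit | 6 | 6/60 = 10.0% | 12/60 = 20.0% |

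The first row is the boundary case, because the last dressing is due off at that visit anyway. After day 7 the loss is the same in every row: one removal costs 4/40 = 10% and two cost 8/40 = 20%.

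**Precision.** The exact (Clopper-Pearson) two-sided 95% upper limit after 0 events in n patients is 1 − 0.025^(1/n):

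- n = 10: 1 − 0.025^(1/10) = 30.8%
- n = 9: 1 − 0.025^(1/9) = 33.6%
- n = 8: 1 − 0.025^(1/8) = 36.9%

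These limits apply to reactions first appearing after day 7, or to all reactions if removed patients also leave the analysis. They are one-sample, patient-level limits. The planned comparison is between sides of the same face. Its loss of precision cannot be computed without reaction rates, beyond noting that the complete late pairs fall from 10 to 9 or 8.

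**How likely a removal is (assumed rates only).** With intolerance rate p, expected removals are 10p and the chance of at least one is 1 − (1 − p)^10:

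- p = 2%: 0.2 expected, 18.3%
- p = 5%: 0.5 expected, 40.1%
- p = 10%: 1.0 expected, 65.1%
- p = 20%: 2.0 expected, 89.3%

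The documents do not say where in this range, or outside it, the true rate lies.

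**The case against.** The strongest reply is that the harm is inferred. The protocol says the patient is removed, but does not say that visits or adverse-event collection then end. The two documents most likely to settle this, Appendices A and I, are not in the text. That stands, and the conclusion is conditional on it.

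It can also be said that the primary endpoint has no stated window, so the amount of primary-endpoint information lost is not established; that no intolerance rate is given; and that moving an upper limit from 30.8% to 33.6% matters little when 10 patients already leave it so wide. All of this stands and limits the size of the point. It does not remove the point: adverse events are to be assessed at every visit to month 3, the visits are already scheduled, and the plan itself puts dressings first among its reasons for stopping.

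A reader might infer more than the documents support:

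- *That the removal rule contradicts the adverse-event section.* It does not. Intolerance can be recorded as an adverse event and the patient then removed. The plan also says all adverse events go to the FDA, so the intolerance itself need not be lost.
- *That removals bias the comparison towards RECELL or towards placebo.* Both sides carry the same dressings and leave together, and nothing in the text links intolerance to skin reactions on either side. Any example of informative loss would rest wholly on assumed rates.

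**Conclusion.** The point holds as a design weakness that is cheap to correct. Followed as written, and unless Appendix A or I provides otherwise, the rule would end study safety observation of already exposed patients by about day 7. Each removal would lose at least four safety visits on both sides of the face, which is 10% of the planned patient-visits after day 7.

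The supported consequence is lost follow-up and a modest loss of precision. The number of removals is unknown and may be zero. The conclusion rests on two readings: that removal from the study ends study visits, and that skin reactions are of interest throughout the visits at which adverse events are assessed. Confidence is medium, because the unseen appendices could answer the first.

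**What to change.** Change only the study-retention part of the rule, and keep two decisions apart: stopping the dressings, and leaving the study.

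- **Withdrawal paragraph (Interventions and Interactions).** State that patients whose dressings are stopped, if they still consent, remain in the scheduled safety visits to month 3.
- **Analytical Plan.** Define the primary safety set as all patients sprayed, and add a patient listing of dressing status and any use of the wash. With so few patients a listing is enough; a second analysis without them is not needed.

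Clinical management of the dressings and the wash, and the right to withdraw, stay as they are. If Appendix A or I already provides these visits, a cross-reference in the withdrawal paragraph would cover the first item.

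The cost is about one sentence in each place, a check that the consent wording agrees, and 4 to 6 already scheduled visits per affected patient. The downside is that the safety set would mix full and interrupted dressing courses and, where the wash was used, shortened exposure. The listing discloses this.
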